1.4 SLS-005 Therapeutic Rationale

1.4.1 Rationale for the study

The nonclinical data generated to date for trehalose support its potential to be used as an effective treatment for ALS. Through its effects on reducing proteinaceous aggregates/inclusions promoting autophagy and lysosomal pathways and reducing cell death, trehalose improved muscle strength and

overall motor skills in animal models of OPMD, SCA3, and ALS. The clinical safety profile of trehalose and the nonclinical toxicology data support the investigation of SLS-005 as a potential treatment of ALS.

1.4.2 Rationale for the Dose, Dosing Regimen, and Route of Administration

If administered orally < 0.5% of ingested trehalose is absorbed into the blood stream. Therefore, to achieve therapeutic blood levels of trehalose, it is necessary to circumvent the metabolism in the human gastrointestinal tract. As such, Seelos has developed SLS-005 an IV formulation of trehalose for injection, 90.5 mg/mL to be used in this study.

In the single ascending dose study of SLS-005 in healthy subjects, the mean weight in the 54 g dose cohort was 74.5 kg. At the dose of 54 g, subjects received 0.72 g/kg. The area under the curve to time infinity (AUC_{inf}) at that dose was $8,595 \pm 2,575$ hour \times $\mu\text{g/mL}$. Since clearance is dependent on body weight (i.e., clearance increases with increasing body weight), in order to achieve a consistent exposure in, at, or near the exposure at the MTD, 54 g/1 hour, a weight-based dose of 0.75 g/kg should achieve an exposure within the clinically acceptable safety range.

One of the proposed mechanisms of action of SLS-005 is to activate autophagy, the blockade of glucose receptors results in a starvation scenario within the cell [25]. Therefore, the MTD will be used to ensure significant exposure. Weekly dosing of SLS-005 is the only regimen to be evaluated in clinical trials to date (patients with OPMD and SCA3) and will be used in this trial.

1.4.3 Rationale for the Patient Population

The pathologic hallmark of the disease is aggregation of proteinaceous inclusions in motor neurons. The main composite of these inclusions is misfolded TDP43 (especially the phosphorylated form), which accumulates in the cytoplasm and is depleted in the nucleus. Patients with either sporadic or familial ALS accumulate TDP43 and patients with the SOD mutation accumulate SOD aggregates and thus have the potential to benefit from treatment with SLS-005 through activation of autophagy.

2.0 SPECIFIC AIMS AND OBJECTIVES

The primary objective of this intermediate expanded access protocol (EAP) is to provide access to the investigational product, SLS-005, to about seventy (70) participants with ALS who are not eligible to participate in clinical trials.

Additional objectives include:

1. Assessment of long-term safety of SLS-005 in a broad population of participants diagnosed with ALS who are not eligible to participate in clinical trials.
2. Assessment of disease progression in a broad population as measured by changes in ALS disease specific measures [ALS Functional Rating Scale-Revised (ALSFRS-R) scores, Slow Vital Capacity (SVC) and ALSAQ-40], and survival.
3. Assessment of markers of neurodegeneration as measured by changes in levels of serum neurofilaments.

3.0 GENERAL DESCRIPTION OF STUDY DESIGN

Planned enrolment is approximately 70 people living with ALS at up to 25 sites in the US. Participants will receive weekly 60- or 90-minute IV infusions of trehalose, 90.5 mg/mL, at a dose of 0.75g/kg at the

study center or at home. This is the same treatment dosage and dosing interval used in regimen E of the HEALEY ALS Platform Trial.

This EAP will enroll two cohorts of participants:

- Cohort 1: participants who do not qualify for any reasonably accessible ongoing clinical trials. This population represents a completely different patient population than that represented in the Platform Trial.
- Cohort 2: participants who have completed the Platform Trial Regimen E RCT and/or OLE and are not eligible for enrollment in another treatment regimen of the platform study. At the completion of their participation in the EAP, these participants may have been exposed to up to 76 weeks of IV trehalose – important long-term safety data.

Specifically, this EAP will capture safety, biomarker, and clinical efficacy data to augment the Phase 2/3 Platform Trial data of IV Trehalose.

4.0 SUBJECT SELECTION

This is a multi-center intermediate-size EAP to provide access to the investigational product, SLS-005. Planned enrollment is about 70 participants at up to 25 sites.

4.1 Inclusion Criteria

1. Sporadic or familial ALS.
2. Age 18 years or older.
3. Cohort 1: Patients do not qualify for any reasonably accessible ongoing clinical trial.
4. Cohort 2: Patients have completed Regimen E RCT and the open label extension (OLE) period of the HEALEY ALS Platform Trial, or completed Regimen E RCT of the HEALEY ALS Platform Trial if the OLE is not available at the site, and are not eligible for enrollment in another treatment regimen of the platform study.
5. Capable of providing informed consent and complying with study procedures, in the Site Investigator's (SI's) opinion.
6. Participants have established care with a physician at a specialized ALS center involved in the study and will maintain this clinical care throughout the duration of the EAP.
7. Participants must have a life expectancy of at least 6 months in SI's opinion (applicable for Cohort 1 only).

4.2 Exclusion Criteria

1. Current diagnosis or healthcare professional-recommended treatment (medication, exercise or diet) of diabetes mellitus.
2. Screening glucose ≥ 140 mg/dl.
3. Known hypersensitivity to trehalose.
4. Current use of oral trehalose.
5. Inability for participant to return to site for weekly drug administration, until approved for home infusions.
6. Screening body weight > 144 kilograms.
7. Participant with a history of any clinically significant or unstable medical condition or lab abnormality that, based on the SI's judgment, may interfere with assessment of the study objectives, safety or full participation.
8. Females who are pregnant or nursing or who plan to get pregnant during the course of the EAP.

9. Females of child-bearing potential, or males, who are unwilling or unable to use highly-effective methods of birth control.
10. Use of investigational treatments for ALS (as part of participation in a clinical trial or another EAP) within 5 half-lives (if known) or 30 days (whichever is longer) prior to the Screening Visit.
11. Permanent assisted ventilation (PAV), defined as more than 22 hours per day of noninvasive or invasive mechanical ventilation for more than seven consecutive days. The date of onset of PAV is the first day of the seven days.
12. Active cancer or history of cancer, except for the following: basal cell carcinoma or successfully treated squamous cell carcinoma of the skin, cervical carcinoma in situ, prostatic carcinoma in situ, or other malignancies curatively treated and with no evidence of disease recurrence for at least 3 years.
13. Presence of unstable psychiatric disease, cognitive impairment, dementia, or substance abuse that would impair ability of the participant to provide informed consent, in the SI's opinion.
14. Patients who choose to take experimental medications and/or supplements, and that is the only reason they are not eligible for trials, won't be eligible for the EAP.

5.0 SUBJECT ENROLLMENT

Screening and Baseline visit assessments and procedures should be completed on the same day. The combined Screening/ Baseline visit may be split into a Screening and a Baseline visit as needed. At Screening, the enrolling investigator will review the protocol procedures and consent form with the participant. The participant will receive a first dose of the IP only after all eligibility assessments are complete and participant eligibility has been confirmed by the investigator.

5.1 Participant Discontinuation

Participants who early terminate from the study will be asked to be seen for an in-person Early Termination Visit and complete a Follow-Up Safety Call. The in-person Early Termination Visit should be scheduled as soon as possible after a participant early terminates. The Follow-Up Safety Call should be completed approximately 28 days after the last dose of study drug.

If the Early Termination Visit occurs approximately 28 ± 7 days after the last dose of study drug, the information for the Follow-Up Safety Call can be collected during the Early Termination Visit, and a separate Follow-Up Safety Call does not need to be completed. If the in-person Early Termination Visit does not occur within 28 ± 7 days of the last dose of study drug, the Follow-Up Safety Call should occur approximately 28 days after the last dose of study drug and the Early Termination Visit will be completed after the Follow-Up Safety Call.

If SLS-005 is stopped because of an adverse event or reaction, the investigator should assess if a visit is needed. Safety labs, vital signs, and medication updates and return should be considered. Follow-up should continue until the adverse event is resolved or stabilized as per the investigator's discretion. If the participant permanently discontinues drug due to an adverse event, then the specific/detailed reason for discontinuation because of an adverse event must be documented in the source documents and the EDC system, and the onset, resolution, severity, relationship, outcome, and treatment required for the adverse event should be recorded as well.

A participant may withdraw from the EAP at any time at his/her own request or may be withdrawn at any time at the discretion of the investigator or designee for safety, behavioral, compliance, or administrative reasons.

If a participant fails to return, or is unreachable, for a scheduled visit within the acceptable visit window, the site staff must make a reasonable attempt to contact the participant to determine the reason for missing the visit and collect any remaining drug.

The following actions must be taken if a participant fails to return to the clinic for a required visit: The site must attempt to contact the participant and reschedule the missed visit as soon as possible and counsel the participant on the importance of maintaining the assigned visit schedule and ascertain whether or not the participant wishes to and/or should continue in the EAP.

Before a participant is deemed lost to follow-up, the investigator or designee must make every effort to regain contact with the participant (where possible, 3 telephone calls and, if necessary, a certified letter to the participant's last known mailing address or local equivalent methods). These contact attempts should be recorded in source documentation.

Should the participant continue to be unreachable, he/she will be considered as lost to follow-up and the site should document all attempts to contact. Their end of participation will be documented as the date of final communication in the opinion of the investigator. If a certified letter or email was sent, the date of the certified letter or email will apply.

Regardless of the circumstance, the detailed/specific reason for participant discontinuation must be recorded in the source documents and the EDC.

Documentation for discontinuation:

Detailed/specific reason for participant discontinuation

- Adverse Event
- Withdrawal of Consent by participant
- Investigator Decision
- Disease progression
- Protocol Terminated by Sponsor
- Lost to Follow-up
- Pregnancy
- Noncompliance
- Death
- Other

5.2 Data Collection and Participants' Identification in NeuroREACH™

The Center for Innovation and Bioinformatics (CIB), Neurological Clinical Research Institute (NCRI) at Massachusetts General Hospital (MGH) introduced the NeuroREACH electronic data capture (EDC) and data repository platform which will be used to collect data for this EAP. The MGH CIB acts as the Data Coordination Center (DCC), and its program management team will oversee this trial for data capture and management. Neurological Global Unique Identifiers (NeuroGUIDs) or their derivatives Neurological System-specific Transactional Anonymous PIN (NeuroSTAmPs) will be generated for each EAP research volunteer to ensure that their participation in a particular program can be tracked across sites for safety purposes. The NeuroREACH platform and participants' data reside on servers located in the Mass General Brigham Enterprise Research Infrastructure and Services (MGB ERIS) server farm that also provides restricted physical and software access to the servers, overall security, and data backup and restoration services.

A NeuroGUID is an 11-character string that is generated using encryption technology licensed by the NCRI from the NIH in 2013. The NeuroGUID is generated on a secure website that utilizes 128-bit Secure Socket Layer (SSL). Of note, this website is managed separately from NeuroREACH. On the website, the NeuroGUID is generated using an irreversible encryption algorithm – it accepts ten identifying data elements (last name at birth, first name at birth, optional middle name, gender at birth, day, month and year of birth, and city and country of birth), and produces a unique, randomly-generated alphanumeric string, or NeuroGUID. No identifying information is stored in the system; it is simply used to generate the NeuroGUID. If the same information is entered into this secure website again, the same NeuroGUID will be returned.

While patient Global Unique Identifiers (GUIDs) and the NIH method of uniquely identifying research participants are somewhat common and acceptable in academia and industry alike, in theory, utilization of GUIDs may lead to an inadvertent re-identification, especially in rare diseases research continuum, as the same volunteer may participate in multiple projects with the same GUID.

Also, when medical data from electronic health records (EHRs) are merged with research data, GUID utilization in EHR systems will make such identifiers as one of HIPAA identifiers, as GUIDs will be stored in the same databases with patients' protected health information (PHI)/personally identifiable information (PII).

Introduction and utilization of NeuroSTAmPs meant to overcome these risks by using unique identifiers (NeuroSTAmPs) per study or resource. The connection between multiple NeuroSTAmPs is established only via application programming interface (API) calls to the NeuroGUID.org server.

NeuroSTAmPs are also useful for sharing de-identified datasets that may still require future re-identification (e.g., based on analysis of clinical information with outside collaborators, more data or tissues are requested for certain research participants). In such cases, generating a new set of NeuroSTAmPs for a single-use purpose encourages collaboration and sharing without exposing NeuroGUIDs to external partners.

NeuroREACH program will use its own set of NeuroSTAmPs to further protect the identity of a research participant. NeuroSTAmP identifiers are created using the same information as in NeuroGUID generation.

6.0 STUDY PROCEDURES

Participants may receive up to 24 weeks of weekly infusions per protocol. Some assessments may be collected remotely, via telemedicine, or over the telephone with site staff.

Participants may be screened over and up to a 21-day period prior to treatment initiation. Participants who meet the inclusion criteria and none of the exclusionary criteria may be enrolled into the EAP. Participants may initiate treatment on the same day as the combined Screening/Baseline Visit, provided consent was obtained and all inclusion and exclusion criteria have been satisfied and eligibility has been confirmed by the investigator prior to treatment initiation.

6.1 Informed Consent

The enrolling investigator will complete the consent form with the participant during the Screening/Baseline Visit.

In some cases, informed consent may be obtained remotely via phone or virtual visit at SI discretion, particularly for participants who have a substantial travel burden to site due to ALS disease progression. Remote consent may only be considered for reconsent, it may not be utilized for the initial consent at the Screening/ Baseline visit unless otherwise specified (see section 6.2.1). The remote consent process will be explained to the participant and will be completed only if participant is in agreement with approach.

The remote consent process will be operationalized as such:

1. The consent form will be provided to the participant electronically or via mail carrier. The consent form will be provided to the participant a minimum of 24 hours prior to consent so there is ample time to review.
2. Consent will be obtained verbally by SI via telemedicine or phone, with sufficient time to review patient risks, potential benefits, and ask/answer questions appropriately.
3. The participant will sign and date (handwritten) their copy of the consent form. If the participant is unable to grip a pen due to hand weakness from ALS, patient will communicate consent verbally or by other preferred communication means. Another party present with the participant will sign as a witness attesting to participant's verbal consent
4. The participant will return the signed clinical consent form back to the site electronically or via mail carrier.
5. The SI will sign and date (handwritten) the consent form and provide a copy of the consent with both signatures back to the participant. Note: the consent form is not considered final and valid until both the participant and the SI have signed.

The site will retain the original clinical consent form signed by both parties and a detailed consent note will be placed in the participant's file.

6.2 Additional Protocol Procedures

The Screening/Baseline Visit and visits at Week 3 and Week 24 are in-person in-clinic visits. The Week 12 visit is remote via telemedicine or telephone with site staff. Vital sign assessments and clinical labs will be collected to assess safety according to the Schedule of Activities and recorded in the source documentation and/ or medical chart. If the visit is done remotely, clinical laboratory samples may be drawn at the study site or obtained at a local site convenient for the participant. Drug dispensation may take place via shipment to the participant from the site for remote visits, as necessary.

6.2.1 Considerations for HEALEY ALS Platform Trial Regimen E OLE Participants

Complete remote participation may be considered for select participants who join from HEALEY ALS Platform Trial Regimen E OLE on a case-by-case basis with permission from the Healey Coordination Center and Sponsor.

In these select cases, remote participation will be operationalized as such:

1. Informed consent (initial and reconsent) will be obtained remotely using the process outlined in section 6.1.
2. Participants will maintain established clinical care with a physician at a specialized ALS center or primary care provider. Participants will maintain ongoing clinical care with visits per standard of care (e.g. approximately every 3 months) throughout the duration of their study participation. The EAP SI will maintain communication with such a local provider and obtain relevant medical records throughout study participation relating to safety monitoring. For example, vital signs including body weight and clinically significant medical changes.
3. All assessments that can be completed remotely/ via telemedicine should be performed. The following assessments may be omitted if necessary: physical exam, neurological exam, vital signs, slow vital capacity, ALSAQ-40, biomarker collection (serum).
4. Clinical laboratory samples must be collected at a local site convenient for the participant.
5. As is allowed for Cohort 2, participants who join from HEALEY ALS Platform Trial Regimen E OLE, home infusions may continue for all 25 infusions. Concurrent assessments such as vital signs, reporting of any infusion related adverse events including Key Study Events and reporting of new concomitant medications should also be done weekly in conjunction with the investigational product infusion.

6.3 Disallowed Medications and Therapies

To date, there are no known pharmacokinetic drug interactions with SLS-005. Participants must not take the following medications while on IP: Oral trehalose is not permitted during the study.

6.4 Visits and Procedures

6.4.1 Screening/Baseline

The Screening/Baseline Visit (Day -21 to 0) is an in-person on-site visit that combines Screening and Baseline procedures. The combined Screening/ Baseline visit may be split into a Screening and a Baseline visit as needed. The following Screening/Baseline Visit procedures (also outlined in the SOA) will be performed prior to the first administration of IP:

1. Informed consent
2. Review Inclusion/ Exclusion criteria
3. Review demographics, ALS and medical history
4. Physical examination, neurological examination
5. Measure vital signs including weight
6. Perform slow vital capacity
7. Administer ALSFRS-R questionnaire
8. Collect ALSAQ-40
9. Collect blood samples for clinical safety labs including HbA1c and serum pregnancy testing for women of childbearing potential (WOCBP)
10. Collect blood samples for biomarker serum collection

11. Review concomitant medications
12. Review adverse events
13. Document infusion-related adverse events
14. Administer the C-SSRS Baseline questionnaire
15. Administer first infusion of study drug after all Screening/Baseline procedures have been completed
16. During each weekly infusion, vital signs associated with the infusion (systolic and diastolic pressure, respiratory rate, and heart rate) are to be measured pre-infusion, 30 minutes (\pm 5 mins) after the start of infusion (SOI), at the end of infusion (\pm 10 mins), and 90 minutes (\pm 10 mins) after the start of infusion. If a participant requires a 90-minute infusion duration due to receiving more than 2 bags of study drug an additional vital signs measurement is to be completed approximately 30 minutes (\pm 10 mins) after the end of the 90-minute infusion. If the infusion is interrupted, vital signs associated with the infusion may be collected at timepoints accounting for the interruption: 30 minutes (\pm 5 mins), 60 minutes (\pm 10 mins), and 90 minutes (\pm 10 mins) after the SOI plus the interruption duration.

6.4.2 Week 1 and Week 2

The Week 1 (Day 7 \pm 3 days) and Week 2 (\pm 3 days) infusion-only visits must occur in-person for Cohort 1 and Cohort 2 participants who join from HEALEY ALS Platform Trial Regimen E RCT, and may occur remotely or in-person for Cohort 2 participants who join from HEALEY ALS Platform Trial Regimen E OLE per site preference. The following visit procedures (also outlined in the SOA) will be performed:

1. Document infusion-related adverse events
2. Administer infusion of study drug
3. Measure vital signs associated with the infusion

6.4.3 Week 3 and Week 24 (or Early Termination)

Week 3 Visit (Day 21 \pm 3 days) and Week 24 (or early termination, Day 168 \pm 14 days) are in-person in-clinic visits that take place following the Screening/Baseline Visit. The following visit procedures (also outlined in the SOA) will be performed:

1. Measure vital signs including weight
2. Perform slow vital capacity (Week 24/ ET only)
3. Administer ALSFRS-R questionnaire
4. Collect ALSAQ-40 (Week 24/ ET only)
5. Collect blood samples for clinical safety labs including HbA1c and serum pregnancy testing for WOCBP (at investigator's discretion)
6. Collect blood samples for biomarker serum collection (Week 24/ ET only)
7. Review concomitant medications
8. Review adverse events
9. Administer the C-SSRS Since Last Visit questionnaire
10. Adjustment of dosing volume based on most recent weight measurement as necessary
11. Administer infusion of study drug
12. During each weekly infusion, vital signs associated with the infusion
13. Determine vital status (Week 24/ ET only)

6.4.4 Week 12

Week 12 (Day 84 \pm 7 days) is a remote telemedicine or telephone visit that takes place following the Screening/Baseline Visit. The following visit procedures (also outlined in the SOA) will be performed:

1. Administer ALSFRS-R questionnaire
2. Review concomitant medications
3. Review adverse events.

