Schedule of Activities – Cohort 1 (Trehalose Naïve Participants)

Activity	Screening/ Baseline Combined ⁷	Week 1, Week 2	Week 3	Week 12	Week 24 or Early Term.	Follow-up Safety Call
	Clinic	In-clinic infusion- only ⁵	Clinic	Telemed/ Phone	Clinic	Telemed/ Phone
	Day -21 to 0	Day 7 ±3, Day 14 ±3	Day 21 ±3	Day 84 ±7	Day 168 ±14	28±7 days after last dose
Written Informed Consent	X					
Inclusion/Exclusion Review	X					
ALS & Medical History	X					
Demographics	X					
Physical Examination	X					
Neurological Exam	X					
Vital Signs ¹	X Weekly documentation of infusion-associated vital signs					
Slow Vital Capacity (SVC)	X				X	
ALSFRS-R	X		X	X	X	
ALSAQ-40	X				X	
Clinical Safety Labs ²	X		X		X	
Biomarker Collection (Serum)	X				X	
Concomitant Medication Review	X		X	X	X	
Adverse Event Review	X		X	X	X	X
Document infusion-related adverse events ³	X Weekly documentation of infusion-related adverse events.					
Columbia-Suicide Severity Rating Scale	X		X		X	
Adjust Dose as Needed ⁴			X			
Administer/Dispense Study Drug ⁵	X Weekly infusions will continue through Week 24. Based on safety and tolerability assessments, infusions may be administered at home after the first 4 in-clinic infusions at Screening/Baseline, Week 1, Week 2, and Week 3.					
Drug Accountability/Compliance ⁶	X Weekly infusions will continue through Week 24. Refer to the Pharmacy Manual, site policy, and GCP guidelines on drug accountability, compliance, and source documentation.					
Vital Status Determination ⁸					X	X

Mass General Brigham Institutional Review Board
Intervention/Interaction Detailed Protocol

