4.1.2 Windowing, Unscheduled Visits and Repeat Test Results

All assessments collected at scheduled and unscheduled visits will be included in the by-participant data listings.

For Safety endpoints, the data will be analyzed according to the nominal visits except Baseline which is defined as last available value prior to the first dose of study treatment. The results collected at scheduled visits per

protocol will be included in the by-visit summary tables. For laboratory data analysis at the scheduled visits, central-laboratory values will (preferentially) be selected for a given visit; however, if there is no non-missing central-laboratory value available and there is a non-missing local-laboratory value collected at the visit, then a local-laboratory value will be used.

In addition, for Safety endpoints of laboratory data, vital signs and C-SSRS assessments, the last assessment during the post-baseline period will also be summarized using the analysis visit name “End of Treatment Period”, which is defined as the last measurement from all post-baseline visits including the unscheduled visits and early termination visit.

For Efficacy and Biomarker endpoints, the protocol defined visit windowing in Table 3 will be used to window the unscheduled visits or early termination visit to scheduled visit when it doesn’t exist. If unscheduled visits or early termination assessments fall in the same window, then select the assessment closest to the target assessment day. If there are two assessments that fall into a visit window and are equidistant from the target assessment day, then the later assessment will be selected.

Table 3 Analysis Visit Windows for Efficacy (ALSF-R, SVC, ALSAQ-40) and Biomarker

Analysis Visit	Nominal Day	Lower Limit	Upper Limit
Baseline	1	None	Time of first dose of study treatment
Week 3	22	19	25
Week 12	85	78	92
Week 24	169	155	183

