4.9.5.3 C-SSRS Assessment

The most severe suicidal ideation and most severe suicidal behavior will be summarized descriptively by visit for each treatment cohort and overall under FAS. In addition, the most severe assessments during the treatment period for suicidal ideation and suicidal behavior will be summarized as well, according to the table below which list the ideation and behavior from most severe to least severe.

Suicidal Ideation Severity	Suicidal Behavior Severity

 • Active suicidal ideation with specific plan and intent • Active suicidal ideation with some intent to act, without specific plan • Active suicidal ideation with any methods (not plan) without intent to act • Non-specific active suicidal thoughts 	
 • Completed suicide • Actual attempt • Interrupted attempt • Aborted attempt

Suicidal Ideation Severity	Suicidal Behavior Severity
• Wish to be dead	• Preparatory acts or behavior

All the C-SSRS assessment information collected will be provided in the data listing.

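### The planned C-SSRS tables do not link on-treatment categories to each participant's own baseline, so new or worsened suicidality can generally be read only as a range

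*Protocol*

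**What the plan says.** Protocol 6.4.1 places "Administer the C-SSRS Baseline questionnaire" before the first infusion, and protocol 6.4.3 places "Administer the C-SSRS Since Last Visit questionnaire" at Week 3 and at Week 24 or early termination. Both Schedules of Activities agree: there is no C-SSRS at the Week 12 call or the follow-up safety call.

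The SAP plans three summaries and a listing:

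- SAP 4.9.5.3, by visit: "The most severe suicidal ideation and most severe suicidal behavior will be summarized descriptively by visit for each treatment cohort and overall under FAS".
- SAP 4.9.5.3, over treatment: "the most severe assessments during the treatment period for suicidal ideation and suicidal behavior will be summarized as well".
- SAP 4.1.2, last value: "for Safety endpoints of laboratory data, vital signs and C-SSRS assessments, the last assessment during the post-baseline period will also be summarized".
- SAP 4.9.5.3 also puts all collected C-SSRS data in a listing.

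SAP Table 1 names C-SSRS among the safety endpoints. The SAP defines treatment emergence for adverse events (4.9.2) and plans change from baseline for vital signs (4.9.4) and HbA1c (4.9.3). It has no baseline-referenced analysis or definition of emergence for C-SSRS.

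**The concern.** The safety question is how many participants developed suicidal ideation or behaviour, or got worse, after starting SLS-005. SAP 4.2 acknowledges that there is no randomised control, and SAP 4.7 limits the historical comparison to survival, ALSFRS-R and vital capacity. For C-SSRS the participant's own baseline is therefore the only comparator, and the planned tables report baseline and post-baseline results as separate margins. A participant with long-standing ideation and one whose ideation began on drug occupy the same cell of the worst-on-treatment table.

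There is a second, smaller issue. The by-visit rows place Week 3 beside Week 24 although the two forms look back over different lengths of time, so the percentages are not directly comparable.

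Nothing is wrong with the protocol steps themselves; the gap is in the SAP.

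**Working it through.** The documents state no figure for C-SSRS, so there is none to reproduce. The check has three parts.

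**1. What unlinked margins say about new onset.** Let N be the number of participants, b the number positive at baseline and w the number positive at worst on treatment. If everyone has both assessments, the number negative at baseline and positive on treatment lies between max(0, w − b) and min(w, N − b). Take N = 70, the planned enrolment; b and w are assumed.

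| b | w | Lower bound | Upper bound |
|---|---|---|---|
| 7 | 10 | 10 − 7 = 3 | min(10, 63) = 10 |
| 7 | 7 | 0 | min(7, 63) = 7 |
| 0 | 7 | 7 | min(7, 70) = 7 |

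The count is exact when nobody is positive at baseline; otherwise the margins generally give a range. Worsening among those already positive is also not determined in general. A cross-tabulation replaces the range by a number.

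**2. Look-back periods.** The schedule gives Week 3 as Day 21 ± 3, Week 12 as Day 84 ± 7 and Week 24 as Day 168 ± 14. Infusion-only contacts are not counted as visits here.

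- Week 3: 21 days nominal, 18 to 24 with the window. Protocol 6.4.1 adds that "The combined Screening/ Baseline visit may be split into a Screening and a Baseline visit as needed". If C-SSRS is done at a split Screening visit on Day −21, this can reach 21 + 24 = 45 days.
- Week 24, if the last visit means the last C-SSRS: 168 − 21 = 147 days. The range is (154 − 24) to (182 − 18) = 130 to 164 days. The nominal ratio to Week 3 is 147/21 = 7.
- Week 24, if it means the Week 12 call: 168 − 84 = 84 days, and the ratio is 84/21 = 4.
- Early-termination assessments share the Week 24 column and can come earlier.

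**3. What unequal look-back can do to the rows.** Suppose every positive is a new event at a constant weekly rate r (assumed). The expected proportion positive over t weeks is 1 − exp(−rt).

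| r per week | 3 weeks | 12 weeks | 21 weeks | Ratio 12:3 | Ratio 21:3 |
|---|---|---|---|---|---|
| 0.1% | 0.30% | 1.19% | 2.08% | 3.98 | 6.94 |
| 1% | 2.96% | 11.31% | 18.94% | 3.83 | 6.41 |

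Under this assumption the Week 24 row is about 4 or 6 to 7 times the Week 3 row with no change in risk. Persistent ideation weakens the effect sharply. Assume 7 of 70 are positive throughout and 5% of the other 63 become positive over 168 days at a constant rate:

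- Week 3: 7 + 63 × (1 − 0.95^(21/168)) = 7 + 63 × 0.64% ≈ 7.4.
- Week 24, 147-day reading: 7 + 63 × (1 − 0.95^(147/168)) = 7 + 63 × 4.4% ≈ 9.8, or about 10.2 if the Week 3 cases also persist.
- The ratio is about 1.3 to 1.4.

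**The case against.** The strongest reply is that the information is not lost. The by-visit table includes a baseline row, so a reader can set it against the worst-on-treatment row and bound new onset. The listing covers about 70 participants with three scheduled assessments each, so each sequence can be traced. Suicidality recorded as an adverse event would enter the TEAE tables, and adverse events are also reviewed at Week 12 and at the safety call. SAP section 2 makes the analyses descriptive, with no trend test planned for C-SSRS. The table shells sit in a separate Data Presentation Plan that was not available.

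Much of this stands, and it sets the size of the point. It does not remove it. The listing supports a derivation by hand, but with no stated definition each reader must make one. Protocol 6.6.8 requires a clinician to be notified after certain positive responses; it does not require an adverse event record. The last-assessment summary in SAP 4.1.2 is not linked to baseline either.

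A reader might infer that emergent suicidality cannot be seen at all. The documents do not support that: the margins bound it, they are exact if nobody is positive at baseline, and the listing is complete. Nor do they support the inference that look-back length alone must produce the pattern across visits. That needs all positives to be new events at a constant rate, and the mixed example gives a ratio of only 1.3 to 1.4.

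It is also fair to object that a shift from the Baseline form to the Since Last Visit form compares two instruments, and the documents do not give the Baseline form's recall period. The fix has to settle that.

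**Conclusion.** The point holds as a minor reporting gap. The planned C-SSRS summaries do not link post-baseline categories to baseline, and the SAP defines no new-or-worsened outcome for this named safety endpoint. The tables therefore generally give a range for new onset, such as 3 to 10 in the example. That example rests on assumed counts, and the range closes as the number positive at baseline approaches zero.

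By-visit percentages at Week 3 and Week 24 are not directly comparable. The nominal ratio of look-backs is 7 or 4, depending on what the last visit means, which the documents do not say.

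One limit remains after any fix. Cohort 2 participants may have received trehalose in the parent trial, and SAP section 7 leaves that trial's data out of this analysis. For them, worse than EAP baseline does not necessarily mean worse than a drug-naive state.

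**What to change.** In SAP 4.9.5.3:

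- Add a shift table of baseline category by worst post-baseline category, separately for ideation and behaviour, by cohort and overall. Include a row and column for no ideation or no behaviour, since the severity list there starts at the mildest positive level.
- Report the number and percentage of participants whose worst post-baseline category is worse than baseline, and state that definition.
- State which recall period of the Baseline form defines the baseline category.
- Note that EAP baseline is not necessarily drug-naive in Cohort 2.

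A footnote on the by-visit table giving each form's look-back would help but is optional.

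The cost is one extra table and a few lines of SAP text. No new data, visits or changes to participant management are needed.
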